3.2 Randomization

Certain baseline factors may have an effect on the primary and secondary endpoints, including the site, age, gender, and the participant's ART regimen at enrolment. In order to minimise bias, randomisation was stratified by:

- Country (Lesotho or Tanzania)
- Age at enrollment ([≥ 6 months to <12 years] vs [≥ 12 years to <19 years])
- ART regimen at enrolment (NNRTI-based, protease inhibitor (PI)-based, or integrase strand transfer inhibitor (INSTI)-based regimen)

In children, gender is unlikely to have a major impact on outcomes. Given the sample size and the relatively even gender distribution (expected female to male ratio approximately

3:2), a strong clustering effect is unlikely. However, gender will be considered in the planned subgroup analysis.

Eligible and consented patients are consecutively enrolled and randomised in a 1:1 ratio to the intervention and control arms. Randomisation is stratified according to the factors listed above, using permuted blocks with varying block size. Randomisation is automated using the MACRO electronic data capture software (Elsevier; see chapters 4.3 Study procedures, and 8.2 Data recording and source data). Randomisation of a participant is performed once eligibility and consent have been confirmed and entered into the database, thereby maintaining concealment of allocation.

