4.1 Confidence intervals and p-values

Statistical tests and confidence intervals will be two-sided. All estimates will be presented with 95% confidence intervals. P-values will be presented where appropriate. No adjustments will be made for multiple testing; interpretations will be based on the strength of evidence of effect size and consistency of results for related outcomes.

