6.2 Analysis methods

Continuous variables will be inspected using histograms: 1) to assess for outliers which may be queried for accuracy, and 2) to assess whether appropriate transformations are required for modeling.

Endpoints will be summarized using medians and interquartile ranges for continuous variables and numbers and percentages for categorical variables, by randomized group. Percentages will be reported to one decimal place.

We will present numbers and proportions of participants achieving each of the four components of the composite endpoint separately. Those with missing VL results will be handled as

described in section 6.1 and reasons for missing VL results will be provided.

For the analysis of the primary outcome, we will use a logistic regression model adjusted for the randomization stratification factors (country, age, and ART regimen; see section 3.2) and relevant baseline characteristics found to be unbalanced between intervention and control clusters (as described above in section 5.5). Results will be reported as odds ratios with 95% confidence intervals. Further, we will estimate the absolute risk difference, with 95% confidence intervals estimated using the delta method [7].

Sensitivity analyses

In a first sensitivity analysis for the primary outcome, we will analyze the PP set (see section 4.2). Protocol violations and deviations will be described. We will summarize the data (numbers and proportions of participants included in this analysis, and meeting the primary endpoint), and fit logistic regression models as for the main primary outcome analysis.

As a second sensitivity analysis of the primary outcome, we will also consider an additional two definitions of viral suppression - <400 and <1000 copies/mL.

Subgroup analysis

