Effect modification of the primary endpoint by country (Lesotho or Tanzania), gender (male or female), age ([\geq 6 months to <12 years] or [\geq 12 years to <19 years]), and ART regimen at enrolment (NNRTI-, PI-, or INSTI-based regimen) will be assessed by incorporating an interaction between arm and the effect modifier acknowledging that power will be low. Regimens at enrolment containing more than one of the above-mentioned ART types will be classified as INSTI-based if they contain at least one INSTI as well as one or more PI(s) and/or NNRTI(s), and as PI-based if they contain at least one PI and one or more NNRTI(s). If there are small numbers of participants within certain subgroups, then such an approach may not be feasible and instead we would restrict the model to the subgroups of sufficient size. If the interaction term is found to be significant, effect estimates will be summarized by subgroup. As the study is not powered for these pre-planned subgroup analyses, these results will be considered exploratory.

Secondary endpoints

For the secondary endpoints defined by the individual components of the composite outcome, we will summarize the number and proportion of participants meeting each endpoint definition as described in 3.1.2. We will follow the same approach as for the main primary outcome analysis if numbers allow, otherwise we will compare the endpoints between the study arms using a chi-squared or Fischer's exact test (in the case of limited events).

For the remaining secondary endpoints, we will follow the same approach as for the main primary outcome analysis if numbers allow. All analyses of secondary outcomes will be done on the mITT set.

Exploratory endpoints

If the number of events is sufficient, the exploratory endpoint of time to documented viral suppression will be assessed using Kaplan Meier estimation and Cox proportional hazard models adjusted for the stratification factors, reporting hazard ratios and 95% confidence intervals.

The exploratory endpoints of drug regimen switches and emergence of new drug resistance mutations will be compared between the study arms using a chi-squared or Fischer's exact test (in the case of limited events).

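### Exploratory endpoints 2 and 3 get only an unadjusted test with no between-arm estimate or interval, although randomisation was stratified by ART class and other endpoints adjust for the strata

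*SAP*

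**What the plan says.** Section 3.2 lists three stratification factors: country, age group and "ART regimen at enrolment (NNRTI-based, protease inhibitor (PI)-based, or integrase strand transfer inhibitor (INSTI)-based regimen"). It adds: "Randomisation is stratified according to the factors listed above, using permuted blocks with varying block size". The stated reason is that "Certain baseline factors may have an effect on the primary and secondary endpoints".

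Section 6.2 then treats the endpoints differently:

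- **Primary endpoint:** "we will use a logistic regression model adjusted for the randomization stratification factors (country, age, and ART regimen; see section 3.2"), reported as an odds ratio and a risk difference, each with a 95% CI.
- **Secondary endpoints:** the same approach where numbers allow. For the components of the composite, a chi-squared or Fisher test is the stated fallback.
- **Exploratory endpoint 1 (time to resuppression):** "Cox proportional hazard models adjusted for the stratification factors, reporting hazard ratios and 95% confidence intervals", if there are enough events.
- **Exploratory endpoints 2 (switches that do not match resistance) and 3 (new mutations):** regimen switches and "emergence of new drug resistance mutations will be compared between the study arms using a chi-squared or" Fisher's exact test if events are limited. This is the only method named, whatever the event count.

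Section 6.2 also promises counts and percentages by arm for every categorical endpoint. Section 4.1 says "All estimates will be presented with 95% confidence intervals" and bases interpretation on effect size and consistency instead of multiplicity control.

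**The concern.** There are two gaps.

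**Strata.** Stratified allocation balances the arms on ART class, so variation between classes largely drops out of the arm comparison. An unadjusted test still counts that variation in its standard error. If class predicts the outcome, the standard error is too large: the test rejects less often than its nominal level and misses some real differences. Endpoints 2 and 3 are defined by switching and by resistance mutations, so ART class is a natural candidate predictor. The SAP gives no reason for dropping it here.

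**Estimate.** A chi-squared or Fisher test returns a p-value. With no between-arm measure named, the interval rule of section 4.1 has nothing to apply to.

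The hypothesis in section 2.2 is that resistance information leads to a switch when there is resistance and avoids one when there is not. Endpoint 2 bears directly on that. If the primary result is null, the size and precision of the difference in endpoint 2 help show whether management changed at all.

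**Working it through.** **Inputs from the SAP.** Total N = 276 (138 is half the sample, section 3.5); 1:1 allocation (3.1); 2 × 2 × 3 = 12 strata (3.2); two-sided tests (4.1); primary event risks of 20% vs 35% (3.3).

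**The plan's own figure.** With pooled variance and no continuity correction, p̄ = 0.275 and

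n = [1.96·√(2·0.275·0.725) + 0.8416·√(0.20·0.80 + 0.35·0.65)]² / 0.15² = (1.2377 + 0.5239)² / 0.0225 = 137.9, so 138 per arm.

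This matches Table 1, as do its other five rows. The SAP gives no event rate or power for exploratory endpoints 2 and 3, and no rate by ART class. All class risks and class shares below are therefore assumptions.

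**Size of the unadjusted test.** Let s be the class shares, p the class risks and p̄ = Σsp. With balance within class,

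r = Σ s·p(1−p) / [p̄(1−p̄)], and true size ≈ 2·[1 − Φ(1.96/√r)].

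Example with risks 60/25/5% and shares 30/30/40%:
- p̄ = 0.18 + 0.075 + 0.02 = 0.275
- numerator = 0.072 + 0.05625 + 0.019 = 0.14725
- denominator = 0.275 × 0.725 = 0.19938
- r = 0.739, 1.96/√r = 2.281, size = 2.3%

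**Simulation, all 276 evaluable.** Pearson chi-squared (χ²) is compared with a Cochran-Mantel-Haenszel (CMH) test stratified by ART class, at two-sided 5%. Rows A: equal class shares, exact balance within class, OR 0.5, 200,000 replicates. Rows B: the 12 strata with permuted blocks of 4 or 6, 6,000 null and 4,000 alternative replicates, and OR = (0.20/0.80)/(0.35/0.65) = 0.464, the plan's primary hypothesis.

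| Assumed class risks (shares) | r | Large-sample size of χ² | Simulated size, χ² vs CMH | Power, χ² vs CMH | Loss, points |
|---|---|---|---|---|---|
| B 15/15/15% (equal) | 1.000 | 5.0% | 4.9 vs 4.8% | 51.6 vs 51.5% | 0 |
| B 25/15/10% (10/30/60) | 0.981 | 4.8% | 5.0 vs 5.2% | 44.5 vs 45.0% | 0.5 |
| B 12/5/2% (10/30/60) | 0.976 | 4.7% | 4.4 vs 4.8% | 15.0 vs 16.2% | 1 |
| B 40/20/10% (20/30/50) | 0.916 | 4.1% | 4.2 vs 5.3% | 53.4 vs 56.3% | 3 |
| A 15/35/55% (equal) | 0.883 | 3.7% | 3.8 vs 5.0% | 64.8 vs 68.7% | 4 |
| A 10/40/70% (equal) | 0.750 | 2.4% | 2.4 vs 4.9% | 56.3 vs 66.5% | 10 |
| B 60/25/5% (30/30/40) | 0.739 | 2.3% | 2.8 vs 5.2% | 53.2 vs 64.0% | 11 |
| A 5/40/80% (equal) | 0.614 | 1.2% | 1.2 vs 5.0% | 41.3 vs 59.7% | 18 |
| B 80/25/5% (30/30/40) | 0.553 | 0.8% | 0.8 vs 4.4% | 34.0 vs 57.5% | 23 to 24 |

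**Simulation, subset only.** Endpoint 3 compares measured resistance at 9 months with baseline, so it may be evaluable only in participants who are still viraemic. As a rough count from the primary risks, 138 × 0.35 + 138 × 0.20 = 48.3 + 27.6 ≈ 76 participants. With the three risk sets of rows A, the unadjusted test's size is then about 3.9% to 4.7%. Power at OR 0.5 is 20 vs 22%, 17 vs 21% and 13 vs 19%, a loss of 2 to 6 points.

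**The case against.** A reader might infer that the unadjusted test is simply too conservative, that the trial's stated error rate is therefore wrong, and that no effect size will be available. The documents do not support any of these.

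- **Conservatism is conditional.** Section 3.2 says only that the baseline factors may matter, and only for primary and secondary endpoints. No switching or resistance rates by class are given. With no class effect the two tests agree, and with a mild gradient or rare events the loss is about 1 point or less. This stands.
- **No error rate is stated for these endpoints.** The 5% level in section 3.3 belongs to the primary endpoint. This stands.
- **The 276-person calculation may not fit endpoint 3.** A genotyped subset formed after randomisation need not keep the stratified balance. The SAP does not say which denominator applies. This stands, and it cuts the loss considerably.
- **Counts and percentages by arm are reported.** A crude difference can be derived from them. What is missing is a specified between-arm estimate with its interval.
- **The error is in the safe direction.** These endpoints are exploratory and were not used to size the trial, and a simple test is defensible for sparse counts. That limits the weight of the point. It does not explain why the simple test is the main method here, when it is only a fallback for the components of the composite.
- **Adjustment is not free.** With few resistance events the logistic model may not be estimable. This stands, so a fallback is needed.

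**Conclusion.** The point holds in a limited form. Two things rest on the text alone and need no assumed rates: endpoints 2 and 3 have an unadjusted test as their only comparison, and no between-arm estimate or CI is specified for them.

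The cost in power depends on how strongly ART class predicts the outcome. With all 276 evaluable, it is 0 points with no class effect, about 3 to 4 with a moderate gradient and about 10 to 18 with a strong to extreme one. The single steepest set tried (80/25/5%) gives 23 to 24. For endpoint 3 the cost is probably much smaller: about 1 point if events are rare, and 2 to 6 in a subset of about 76. The class risks, the class shares and the subset size are assumptions.

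The plan does not inflate type I error here, and the primary conclusion is unaffected. This is a worthwhile improvement and not a threat to the trial's main result.

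**What to change.** In section 6.2, under exploratory endpoints, replace the single test for endpoints 2 and 3 with three steps:

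1. Where numbers allow, use the logistic model already specified for the primary outcome, adjusted for country, age and ART class. Report the odds ratio and the risk difference, each with a 95% CI.
2. If events are few, use a Mantel-Haenszel test and a risk difference stratified by ART class, with a 95% CI.
3. If counts are very sparse, use Fisher's exact test with an unadjusted risk difference and its 95% CI.

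This needs a few lines of text, no new data and slightly more analysis work. The one real drawback is that the adjusted model may not be fittable with sparse events, which steps 2 and 3 cover.

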6.3 Missing data

Where applicable, percentages of baseline and endpoint data will be of non-missing values, with the number (%) of missing values given if data are not complete. As detailed in section 6.2, main analyses of the primary and the secondary outcomes (with the exception of virological failure) will include all participants as randomized with missing virological data counted as failures.

For the secondary outcome of unobserved virologic failure, only individuals with a valid viral load result in the specified window will be included in the analysis.

Where significant amounts of data are missing in important covariates, we may consider multiple imputation as sensitivity analyses if necessary and compare results to models ignoring missing data [8].

6.4 Additional analyses

Two nested studies about cost-effectiveness and drivers of viremia will be analysed separately.

6.5 Harms

Safety data is collected and serious adverse events will be summarized by study arm. Further details about safety procedures and reporting are described in the protocol.


8. Shell tables

Presented below are the shell tables for the baseline characteristics, to illustrate the variables included.

Table 8.1. Baseline characteristics by group: demographic

	Variable	Control	Intervention	Total
Number randomized (mITT)	arm			
Country	Stsite_der			
Tanzania				
Lesotho				
Age, years	age			
≥6 months to <12 years	agegr_der			
≥12 years to <19 years				
ART regimen	regimen_der2			
NNRTI-based				
PI-based				
INSTI-based ¹				
Sex, female	sex			
Primary caregiver	care			
Both parents				
Mother				
Father				
Grandparent(s)				
Other				
Parent vital status				
Mother alive	mothervit			
Father alive	fathervit			
Treatment supporter (other than caregiver)	trtsup			
Yes				
No				
Unknown				
Main transportation to health facility	travmod			
Walk				
Ride horse/donkey				
Taxi/Public transport				
Bicycle				
Own or borrowed motorized vehicle				
Other				
Cost of health facility visit				
One-way travel time	travtim			
One-way travel cost	travcost			
Tanzania (TZS)	curr			
Lesotho (LSL/ZAR)				

Results are n (% of those with non-missing data) for categorical variables and median (IQR) for continuous variables.

¹ In cases where an individual was on a PI and INSTI, they were categorized as being on an INSTI-based regimen.

Table 8.2. Baseline characteristics by group: clinical

	Variable	Control	Intervention	Total
Number randomized (mITT)				
Time since HIV diagnosis (years)	time_since_hiv_yrs			
Time since ART start (years)	time_on_art_yrs			
WHO stage at ART initiation	whoart			
T1				
T2				
T3				
T4				
Unknown				
CD4-based immunodeficiency at ART initiation	Cd4artyn, cd4artpcyn			
Available				
No/no significant				
Mild				
Advanced				
Severe				
Weight, kg	wt			
Height, cm	ht			
MUAC (cm) [1]	muac			
Nutritional status	nutrst			
Not malnourished				
Mild				
Moderate				
Severe				
Overweight/obese				
Nutritional supplement	nutrsup			
Therapeutic				
Supplemental				
Both				
Neither				

Results are n (% of those with non-missing data) for categorical variables and median (IQR) for continuous variables.

Table 8.3. Baseline characteristics by group: laboratory.

	Variable	Control	Intervention	Total
Number randomised				
CD4-based immunodeficiency at baseline				
Available				
No/no significant				
Mild				
Advanced				
Severe				
HbsAg				
Positive				
Negative				
Haemoglobin				
Leucocyte				
Platelets				
Serum Creatinine				

Results are n (% of those with non-missing data) for categorical variables and median (IQR) for continuous variables.

[1] Only measured in those aged 6 months to 5 years.

Table 8.4. Primary outcome

	N	Control N (%)	Intervention n (%)	Odds Ratio (95% CI)	Risk difference (95% CI)
Number randomized					
mITT					
PP set
